23 STUDY MONITORING AND EARLYSTOPPING RULES

To ensure the safety of the proposed treatment in the neoadjuvant setting, precautions have been taken into consideration and implemented:

- A careful review of the literature has demonstrated that the use of neoadjuvant chemotherapy does not increase surgical morbidity or mortality (14). Because single agent M7824 has been found to have a more favorable adverse event profile than single agent chemotherapy (38, 39) it is expected that neoadjuvant immunotherapy will be feasible and safe.
- A Bayesian method to monitor the toxicity in the perioperative phase will be used (40)

Unacceptable toxicity is defined as: severe pneumonitis precluding performance of planned surgical resection, death during neoadjuvant treatment or within 30 days aftersurgery; severe post op acute respiratory distress syndrome (ARDS) not attributable to aspiration requiring prolonged ventilator support; development of broncho-pleural fistula not attributable to surgical technique; wound healing delays that require management with a major surgical procedure; wound infections that require intravenous antibiotic use for more than 21 days; re-operation for bleeding or infection deemed secondary other factors than surgical technique; empyema; stroke or myocardial infarction within 30 days after surgery; any treatment-related adverse events leading to a delay in surgery resulting in > 8 week interval between the last dose of neoadjuvant therapy and surgery, any surgical complication that is considered major by the treating physician and possibly, probably or definitely related the immunotherapy medications. The incidence of surgical complications for thoracoscopy/thoracotomy for non-small cell lung cancers is approximately 16-31% (41). We consider that neoadjuvant therapy with either one of the regimens is not feasible if it results in unacceptable toxicities in at least 20% of the patients with 70% or higher probability.

We consider that neoadjuvant therapy with either one of the regimens is not feasible if it results in unacceptable toxicities in at least 20% of the patients with 70% or higher probability. The toxicity monitoring will start after a minimum of 6 patients have been enrolled with known toxicity outcome. With a prior probability of toxicity as Beta(0.2,0.8), the toxicity stopping boundaries are defined as seeing unacceptable toxicity in ≥ 3 of 6-8, 4 of 9-12, 5 of 13-16, 6 of 17-20 or 7 of 21-23 patients. When the true toxicity rates are 0.1, 0.2, and 0.35, the probabilities of early stopping are 0.06, 0.34, and 0.84 with the corresponding average sample sizes of 22.2, 18.6, and 11.2, respectively. In case one arm needs to be closed due to excessive toxicity, accrual to the remaining arm will continue in a non-randomized way. The calculation was performed using the Shiny Application: Bayesian Toxicity Monitoring version 2.1 (<http://ibl.mdanderson.org/BTM/>).

The Investigator is responsible for completing an efficacy/safety summary report, and submitting it to the IND Office Medical Affairs and Safety Group, for review and approval. This should be

Clinical Study Protocol 9.0
Bintrafusp Alpha- M7824
submitted after the first 6 evaluable patients per study arm, complete 30 days after surgery, and
every 3 evaluable patients per arm, thereafter.

MDA Cancer Center
15 June 2020

A copy of the cohort summary should be placed in the Investigator's Regulatory Binder under
"sponsor correspondence".

24 Data Confidentiality Plan

Confidentiality of Data

All clinical and research information/data will be collected and placed in our institution's Data Management Initiative (DMI) supported by Biostatistical Department under [name] oversight. This is a secured, password-protected intranet-based (UTMDACC only) database. Access to this database is restricted to the PI, protocol research nurse, protocol research data coordinator and DMI database analyst.

The investigator affirms that information as pertains to the study will be maintained in confidence, and such information will be divulged to the IRB, IEC, or similar or expert committee; affiliated institution and employees, only under an appropriate understanding of confidentiality with such board or committee, affiliated institution and employees. Data generated by this study will be considered confidential by the investigator, except to the extent that it is included in a publication.

Confidentiality of Participant Records

The investigator agrees that the Sponsor (or Sponsor representative), IRB/IEC, or regulatory authority representatives may consult and/or copy study documents to verify worksheet/CRF data. By signing the consent form, the participant agrees to this process. If study documents will be photocopied during the process of verifying worksheet/CRF information, the participant will be identified by unique code only; full names/initials will be masked prior to transmission to the Sponsor. The investigator agrees to treat all participant data used and disclosed in connection with this study in accordance with all applicable privacy laws, rules and regulations.

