9. TREATMENT

9.1 Induction Treatment

Patients will receive induction treatment, as follows:

Arm A: M7824 1200 mg intravenously (IV) on days 1, 15, and 29

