9.2 Surgery

Surgery will be performed after completion of induction therapy. It is strongly recommended that 3 doses of M7824 (Arm A) are administered prior to surgery. However, less than 3 doses of M7824 will be allowed in case of excessive toxicities or other reasons identified by the treating physician that may lead to an unfavorable benefit/risk ratio of proceeding with therapy as planned per protocol, after discussing the case with the principal investigator.

There must be at least 4 to 6 weeks M7824-free interval before surgery (i.e., surgery will only be performed at least 4 to 6 weeks after the last dose of M7824, unless there is a strong clinical indication to perform surgery sooner, in the opinion of the treating physician). It is strongly recommended that surgery be performed within 4 to 6 weeks after the last dose of M7824 induction therapy.

The operative approach (thoracoscopy versus thoracotomy) and the extent of surgical resection will be based on the treating surgeon's judgment and may include wedge resection, segmentectomy, lobectomy, or pneumonectomy with mediastinal lymph node dissection of nodal stations 4, 7, 8, 9, 10, 11-14 for right sided resections, and nodal stations 5, 6, 7, 8, 9, 10, 11-14 for left sided resection.

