21 STUDY ASSESSMENTS AND PROCEDURES

Baseline evaluation:

Investigations	Timing		
History and Physical Exam including:	Treatment history Medical history Smoking history Height and weight	Vital signs ECOG PS TNM stage	Within 14 days prior to treatment initiation
Current Smoking Status and Tobacco Use	Assessment of patient's current smoking status and tobacco use		Within 14 days prior to treatment initiation
Symptoms & Toxicities	Evaluation and documentation of symptoms and toxicities using the NCI CTCAE v5.0		Within 14 days prior to treatment initiation
Concomitant Medications	Documentation of concomitant medications		Within 14 days prior to treatment initiation
Hematology and Coagulation	CBC with hemoglobin, platelets, and WBC with differential Prothrombin time (PT) / Partial thromboplastin time (PTT)		Within 14 days prior to treatment initiation
Biochemistry	Albumin Alkaline phosphatase Potassium Total bilirubin, direct, indirect BUN Creatinine Total protein Free T4, TSH	Glucose LDH SGOT (AST) SGPT (ALT) Sodium Magnesium Uric acid	Within 14 days prior to treatment initiation

Pregnancy Test	Urine or serum (for women of childbearing potential only)	Within 48 hours prior to treatment initiation
Radiology	CT chest	Within 30 days prior to treatment initiation
Radiology	PET-CT	Within 60 days prior to treatment initiation
Radiology	MRI brain or CT brain (only for patients with stage II or III on pre-operative staging)	Within 60 days prior to treatment initiation
Mediastinal staging	CT chest / PET-CT, mediastinoscopy, and/or endobronchial ultrasound	Within 60 days prior to treatment initiation
Pulmonary tests	Complete pulmonary function test	Within 60 days prior to treatment initiation
Tumor/Adjacent Lung Tissue Collection for Biomarkers	Archival tissue or new biopsy of primary tumor for biomarker analysis (optional) Tissue obtained for mediastinal staging (optional)	Prior to treatment initiation
Blood-based biomarkers	Blood sample	Prior to treatment initiation
Stool-based Microbiome	Stool sample	Prior to treatment initiation
Pharmacokinetic (PK) studies	Blood sample	Prior to infusion and immediately after infusion of dose #1 of M7824
Anti-Drug Antibodies (ADA) studies	Blood sample	Prior to infusion of dose #1 of M7824

Evaluation during neoadjuvant treatment (prior to each M7824 infusion):

Investigations		Timing	
Physical Exam Including:	BSA Vital signs	Within 7 days prior to dose #2 and #3 of M7824	

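### The unacceptable-toxicity definition lists stroke and infarction only after surgery and does not clearly count deaths between the last dose and surgery, or after the last dose in patients never operated on

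*Combined protocol and SAP*

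**What the plan says.** Section 23 defines unacceptable toxicity by a list of events, and the number of patients with such an event is compared with a stopping boundary. Four items matter here:

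- Death: "death during neoadjuvant treatment or within 30 days aftersurgery".
- Cardiovascular events: "stroke or myocardial infarction within 30 days after surgery".
- Pneumonitis: "severe pneumonitis precluding performance of planned surgical resection".
- Delay: "any treatment-related adverse events leading to a delay in surgery resulting in > 8 week interval" between the last neoadjuvant dose and surgery.

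The remaining items concern post-operative or surgical complications.

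Section 9.1 schedules "M7824 1200 mg intravenously (IV) on days 1, 15, and 29". Section 9.2 says "Surgery will be performed after completion of induction therapy" and adds "There must be at least 4 to 6 weeks M7824-free interval before surgery", with an exception for a strong clinical reason to operate sooner. No section defines when neoadjuvant treatment ends.

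Section 23 starts the monitoring once 6 patients have a known toxicity outcome. The accompanying safety summary is due when the first 6 evaluable patients are 30 days past surgery, and after every 3 evaluable patients from then on. The term evaluable is not defined, and nothing says how a patient who never has surgery enters the count.

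**The concern.** The listed windows do not join up. Stroke and infarction have only a post-operative window. Death has two windows, and the end of the first is undefined. Between the last dose and the operation lies an interval in which a late immune-related or cardiovascular event could occur. A patient whose surgery is cancelled has no post-operative clock at all.

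The boundary works on small counts, so each patient needs one unambiguous score. The error can go only one way: an event left out lowers the count and favours continuing. Section 22 rules out interim futility and efficacy monitoring, so no other numerical rule would pick up the omission.

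**Working it through.** **1. Length of the interval.** The last planned dose is on day 29. Surgery 28 to 42 days later falls on days 57 to 71, which is 56 to 70 days after the first dose. If neoadjuvant treatment ends with the last dose, the interval is 28/56 = 50% to 42/70 = 60% of the time from first dose to surgery.

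**2. How each event is scored under Section 23 as written.**

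| Event | Scored as unacceptable toxicity? |
|---|---|
| Death during dosing, surgery or not | Yes, death item |
| Severe pneumonitis that prevents resection | Yes, pneumonitis item |
| Non-fatal stroke or infarction before surgery, including during dosing | Not in its own right; yes if treatment-related and surgery is delayed beyond 8 weeks |
| The same, with surgery cancelled | Unclear: the delay item has no interval to measure |
| Death between last dose and surgery | Depends on what neoadjuvant treatment means, unless it follows qualifying pneumonitis |
| Death after last dose, never operated on | As above |
| Death, stroke or infarction within 30 days after surgery | Yes |

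**3. Which reading of neoadjuvant treatment the protocol supports.** Section 21 points both ways. Its table headed "Evaluation during neoadjuvant treatment (prior to each M7824 infusion" ties the phrase to dosing, and a footnote to that table describes patients at the later pulmonary function test as being past neoadjuvant therapy. Yet the same table holds the CT, PET-CT, pharmacokinetic, antibody and pulmonary assessments made at least 14 days after the last dose, and the schedule has no separate block between that table and surgery.

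**4. Reproducing the plan's figures.** Inputs from Section 23: stop at 3 of 6-8, 4 of 9-12, 5 of 13-16, 6 of 17-20 or 7 of 21-23. Let f(n, x) be the probability of reaching patient n with x events and no earlier stop:

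f(n, x) = (1 - p) f(n-1, x) + p f(n-1, x-1)

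From n = 6, states at or above the boundary are removed and added to the stopping probability.

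| True rate p | Printed stopping probability | Recomputed, crossing at 23 not counted / counted | Printed average N | Recomputed average N |
|---|---|---|---|---|
| 0.10 | 0.06 | 0.054 / 0.054 | 22.2 | 22.2 |
| 0.20 | 0.34 | 0.337 / 0.344 | 18.6 | 18.6 |
| 0.35 | 0.84 | 0.841 / 0.854 | 11.2 | 11.2 |

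The printed figures reproduce to within 0.01 when a crossing at patient 23 is not counted.

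**5. Effect of uncounted events.** If m percentage points of the true rate go uncounted, the rule runs at p - m. The documents give no value for m, so it is an assumption shown as a range. At a true rate of 0.25, counting a crossing at patient 23 as a stop:

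| m (points) | Rate the rule sees | Stopping probability | Average N |
|---|---|---|---|
| 0 | 0.250 | 0.54 | 16.0 |
| 0.3 | 0.247 | 0.53 | 16.1 |
| 1 | 0.240 | 0.50 | 16.5 |
| 5 | 0.200 | 0.34 | 18.6 |

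**6. A single event.** At 6 patients, 3 events stop the trial and 2 do not, so one uncounted event reverses the decision. The synopsis prints other boundaries, but they also require 3 of 6. The printed Section 23 boundaries are used here as they stand. They do not follow from the stated 70% cutoff (2 of 6 under Beta(0.2, 0.8) already gives 0.72), which is a separate matter to reconcile.

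**The case against.** A reader might infer that every fatal or cardiovascular event before surgery, and every such event in an unoperated patient, is excluded. The documents do not support that. Death during dosing counts whether or not surgery follows. Severe pneumonitis that prevents resection counts by definition in an unoperated patient. A treatment-related stroke or infarction counts if it pushes surgery past 8 weeks. The Section 21 layout allows a wider reading under which interval deaths count too. For deaths, then, this is an ambiguity and not an exclusion, and the 50% to 60% in step 1 applies only on the narrow reading. For pre-operative stroke and infarction the wider reading does not help, because their window is stated outright.

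The trial also has other safeguards. Section 5.1 provides for discontinuation if the risk-benefit ratio deteriorates, Section 23 requires safety summaries for review by the IND Office, and Appendix 2 requires a report within 24 hours for fatal or life-threatening events that are unexpected and related. An interval death would be seen. That stands, but none of these feeds the boundary.

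Finally, such events may be rare. Section 3.7 reports one Grade 5 hemolysis among 377 subjects (0.3%) and no Grade 4 or 5 immune-related events; Section 3.9 reports no treatment-related deaths among 80 NSCLC patients. These figures cover related events only, so they are not a ceiling, but they give no support for treating 5 points as the expected loss.

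**Conclusion.** The concern holds in this form: a non-fatal stroke or infarction before surgery, including during dosing, is not counted unless the delay item catches it, and a death after the last dose but outside the post-operative window has no definite score unless it follows qualifying pneumonitis. Any resulting error favours continuing.

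The size depends on an unknown rate. At a true rate of 25%, the loss in stopping probability runs from about 0.01 (0.3 points uncounted) to 0.20 (5 points uncounted), with the upper end resting wholly on the assumption. The one-event reversal at 6 patients needs no assumed rate. It requires only that one of three affected patients has an event outside the listed windows.

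**What to change.** In Section 23:

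1. Count death, stroke or myocardial infarction at any time from the first dose of M7824 through 30 days after surgery.
2. For patients never operated on, count these events within a follow-up window that the sponsor fixes in advance. The 100-day SAE window in Appendix 2 is one option already in the protocol. It is open to debate: it would take in deaths from progression, and it is longer than the window for operated patients, which ends about 28 + 30 = 58 to 42 + 30 = 72 days after the last dose. The sponsor should therefore state whether deaths clearly due to progression are excluded.
3. State that unoperated patients stay in the denominator and have a known toxicity outcome at the event or at the end of that window.

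The cost is a few sentences. If the window does not exceed 100 days after the last dose, SAE reporting already covers it. The rule may stop somewhat more often, and the printed operating characteristics would then apply to the wider event definition.

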
Toxicity monitoring: A Bayesian method to monitor the toxicity in the perioperative phase will be used. We consider that neoadjuvant therapy with either one of the regimens is not feasible if it results in unacceptable toxicities in at least 20% of the patients with 70% or higher probability. The toxicity monitoring will start after a minimum of 6 patients have

been enrolled. With a prior probability of toxicity as Beta (0.5,0.5), the toxicity stopping boundaries are defined as seeing unacceptable toxicity in ≥ 3 of 6-7, 4 of 8-10, 5 of 11-13, 6 of 14-16, 7 of 17-19, 8 of 20-22 or 9 of 23 patients. When the true toxicity rates are 0.1, 0.3, and 0.5, the probabilities of early stopping are 0.04, 0.56, and 0.97 with the corresponding average sample sizes of 22.4, 15.1 and 8.0, respectively.

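### The operating characteristics of the section 23 toxicity rule assume immediate outcomes, but the schedule implies a lag of about 86–100 days, and the plan does not say whether accrual is held while outcomes are pending

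*Combined protocol and SAP*

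**What the plan says.** Section 23 gives a Bayesian boundary for unacceptable toxicity: stop at 3 or more of 6–8 patients, 4 of 9–12, 5 of 13–16, 6 of 17–20, or 7 of 21–23. At true rates of 10%, 20% and 35%, "the probabilities of early stopping are 0.06, 0.34, and 0.84 with the corresponding average sample sizes of 22.2, 18.6, and 11.2, respectively".

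On timing, the same section says: "The toxicity monitoring will start after a minimum of 6 patients have been enrolled with known toxicity outcome". A safety report goes to the IND Office, "submitted after the first 6 evaluable patients per study arm, complete 30 days after surgery", and then after every third evaluable patient. The definition of unacceptable toxicity mixes early events, such as "severe pneumonitis precluding performance of planned surgical resection, death during neoadjuvant treatment", with later ones, such as "stroke or myocardial infarction within 30 days after surgery" and a related adverse event "leading to a delay in surgery resulting in > 8 week interval between the last dose of neoadjuvant therapy and surgery".

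The only sentence in section 23 about accrual concerns a closed arm: "In case one arm needs to be closed due to excessive toxicity, accrual to the remaining arm will continue in a non-randomized way". It does not deal with pending outcomes.

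The synopsis starts monitoring after 6 patients are enrolled, without asking for a known outcome, and gives a different prior: "been enrolled. With a prior probability of toxicity as Beta (0.5,0.5), the toxicity stopping boundaries are defined as" a different set of limits. Its averages, at other true rates, are 22.4, 15.1 and 8.0.

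Accrual is put at about 2 a month in the synopsis and 2–3 a month in section 22. Both give an accrual period of 15–24 months for 23 patients.

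**The concern.** The average sample size tells a reader, and the office reviewing safety, roughly how many patients will be treated before a harmful regimen is stopped. If outcomes take about three months while patients keep entering, the number whose outcomes are known at a stop is smaller than the number enrolled. The printed average then describes the first quantity and is easily read as the second. The gap grows with the accrual rate, so a conflict in the accrual figures leaves its size undetermined. The probability of stopping is also affected if events enter the count sooner than non-events, because the observed toxicity fraction is then temporarily inflated.

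**Working it through.** **1. Reproduce the printed figures.** Inputs: the section 23 boundary, a maximum of 23 patients, a look after every patient from the sixth, and each outcome known before the next entry. An exact binomial recursion gives s_n, the probability of first crossing at patient n. The average is Σ n·s_n + 23·(1 − Σ s_n).

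| True rate | P(stop), looks to 22 | P(stop), looks to 23 | Average n | Printed |
|---|---|---|---|---|
| 10% | 0.054 | 0.054 | 22.24 | 0.06; 22.2 |
| 20% | 0.337 | 0.344 | 18.56 | 0.34; 18.6 |
| 35% | 0.841 | 0.854 | 11.23 | 0.84; 11.2 |

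The averages agree to the printed decimal. The printed set is therefore the immediate-outcome set.

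**2. Derive the lag.** Doses are on days 1, 15 and 29 (section 9.1), so first to last dose is 28 days. Surgery is recommended 4–6 weeks after the last dose (section 9.2): 28–42 days. The post-operative point is 30 days (the section 23 report trigger, and the death and stroke/infarction criteria). The total is 28 + 28 + 30 = 86 to 28 + 42 + 30 = 100 days.

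**3. Derive the accrual range.** 23/3 = 7.7 and 23/2 = 11.5 months, both outside 15–24. Conversely, 23/24 = 0.96 and 23/15 = 1.53 patients a month.

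**4. Outcomes counted only at the end of the window, no hold, even entry.** Patients entering during the lag: m = floor(rate × lag / 30.44). For example, 2 × 86/30.44 = 5.65 gives m = 5, and 3 × 100/30.44 = 9.86 gives m = 9. So 11–15 patients are already enrolled when the sixth outcome is known at 2–3 a month. Average enrolled = Σ s_n·min(23, n + m) + 23·(1 − Σ s_n). At 35%, for lags of 86 and 100 days:

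| Rate per month | m | Average enrolled | P(stop before all 23 enrolled) |
|---|---|---|---|
| 0.96 | 2, 3 | 12.9, 13.7 | 0.83, 0.81 |
| 1.53 | 4, 5 | 14.6, 15.3 | 0.79, 0.78 |
| 2 | 5, 6 | 15.3, 16.1 | 0.78, 0.78 |
| 3 | 8, 9 | 17.7, 18.4 | 0.72, 0.70 |

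Over the same rates the average is 22.4–22.7 at 10% and 19.2–21.4 at 20%. The chance of ever crossing is unchanged from step 1, because patients are still counted in enrolment order.

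**5. Events counted at once, non-events at the end of the window, no hold.** Assumption: an event falls at a uniformly random time in the window. Simulation with 40,000 runs per case, same rates and lags (last digits subject to simulation error):

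| True rate | Average enrolled | P(ever crossing) |
|---|---|---|
| 10% | about 22.1 | 0.07–0.12 |
| 20% | 18.4–19.0 | 0.38–0.52 |
| 35% | 11.7–14.9 | 0.87–0.92 |

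At 35% the chance of stopping before all 23 are enrolled is 0.86–0.90, above the printed 0.84.

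**6. Check which rule the boundary represents.** With Beta(0.2, 0.8) and 2 of 6 events, the posterior is Beta(2.2, 4.8) and P(rate > 0.20) = 0.72. The stated 0.70 cutoff would therefore stop at 2 of 6, while section 23 prints 3. A 0.80 cutoff reproduces every printed limit. A 0.70 cutoff gives 2 of 6, 3 of 7–10, 4 of 11–14, 5 of 15–19 and 6 of 20–23.

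**The case against.** Immediate-outcome operating characteristics are a common presentation, and section 23 does not call its averages numbers enrolled. Counting every outcome at the end of the window is an extreme: pneumonitis that precludes surgery, or death during treatment, is known early, and serious events are reported to the IND Office within days (Appendix 2). This stands, and it limits the claim. A reader might infer that the lag always means more patients enrolled and a weaker rule. The calculations do not support that. With events counted at once, average enrolment is slightly lower at 10% and about unchanged at 20%, and an early stop at 35% becomes more likely.

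A reader might also take 86–100 days as a protocol figure. It is derived from a recommended timeline. Within the toxicity definition, 30 days is attached only to death and to stroke or infarction; other events, such as empyema or fistula, carry no stated window.

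Finally, the 15–24 months might be read as evidence that a hold was planned. A simulated hold, under which no patient enters while pending outcomes could already have crossed the boundary, gives mean accrual of about 16–19 months at 10% toxicity and 19–23 at 20%, at 2–3 a month. But 46 patients in two arms at 2–3 a month also take 15.3–23 months, and section 23 still refers to a remaining arm. Neither explanation is stated, so the documents settle neither. Equally, silence about a hold does not show that accrual will continue.

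**Conclusion.** The point holds in this form. The printed stopping probabilities and averages are valid only for immediate outcomes, and the plan does not state the accrual and counting rules needed to know what applies with the lag. If accrual is not held, average enrolment at 35% toxicity exceeds 11.2 under both counting rules, by about 0.5 to 7 patients (11.7 − 11.2 to 18.4 − 11.2). At 10% and 20% no general direction can be claimed. Counting events at once mainly raises the probability of stopping, from the printed 0.06 and 0.34 to 0.07–0.12 and 0.38–0.52.

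These sizes rest on even accrual, looks after every patient, the section 23 boundary as printed and, for the second rule, uniform event times. They are provisional until the boundary is settled. The inconsistency between accrual rate and accrual period depends on none of these assumptions, although an unstated hold would remove it.

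**What to change.** 1. Reconcile the prior, cutoff and boundary between the synopsis and section 23, since every operating characteristic depends on them.
2. State whether accrual continues or is held while outcomes are pending. That choice is the sponsor's.
3. State when a patient with an event and a patient without one enter the count, define evaluable, and use one starting condition in both places.
4. If accrual continues, restate the stopping probabilities and the average number enrolled with the lag. Alternatively, label the printed figures as assuming immediate outcomes and give the lagged ones beside them. If accrual is held so that no patient enters while pending outcomes could already have crossed the boundary, say so; immediate-outcome figures for the reconciled boundary then apply.
5. Correct the accrual rate or the accrual period in the synopsis and section 22 so that they agree for 23 patients.

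The cost is wording and a short calculation, with no added patients or procedures. If accrual continues, the stated averages at high toxicity become less favourable. If it is held, accrual takes longer, as in the simulated hold above.
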